## **6.6** Treatment Compliance

A participant is considered compliant with the study protocol when study medication is administered at a compliance level of  $\geq 80\%$  (excluding dose holds for surgical operations or drug-related AEs).

Compliance will be calculated using the following equation:

([Number of capsules ingested] / [Number of capsules that should have been ingested]) \*100%

#### 6.7 Blinding

This is an open-label study. Neither the participant nor the investigator or site staff will be blinded to the treatment administered.

#### 6.8 Concomitant Medication and Procedures

#### **6.8.1** Permitted Treatment

The following treatments are permitted while on study:

- Standard therapies, including sclerotherapy, for concurrent medical conditions
- Oral hypoglycemic treatment or insulin for elevated blood glucose
- Topical or low dose systemic steroid treatment
- High dose steroid treatment is permitted when used intermittently for acute exacerbation of disease
- Factor Xa inhibitors (fondaparinux, rivaroxaban, apixaban, and edoxaban) are preferred to warfarin if anticoagulation therapy is needed
- Surgical procedures are allowed, provided that in the opinion of the investigator, the participant does not meet criteria for treatment discontinuation
  - A minor surgical operation or procedure generally does not require extensive resection (eg, biopsy, tooth extraction, etc.) and hospitalization (eg, day surgical operation), presents low risk of complications, and may not require treatment interruption. If drug hold is required, the investigator and the Sponsor should discuss the duration of drug hold before and after the surgical operation.
  - A major surgical operation requires a more extensive resection (eg, appendectomy, tumor excision), prolonged hospitalization with higher risk of complications, and treatment interruption for at least 2 weeks before and 1 week after the surgical operation. If a surgery is required, the investigator and the Sponsor should discuss the duration of drug hold before and after the surgical operation.

#### **6.8.2** Prohibited Treatment

The following treatments are prohibited while on study:

- Other investigational agents
- Inhibitors of the mTOR pathway (eg, sirolimus, everolimus)
- Immunosuppressive therapies

· Continuous high dose steroids

## 6.8.3 Medications to be Avoided While on Study

Miransertib is metabolized by CYP2D6, CYP2C9, and CYP3A4. Additionally, miransertib has been shown to inhibit CYP2C19, CYP2C9, and CYP2D6 with IC50 values of 4.0, 3.0, and 10.2 μM, respectively.

A preliminary assessment of the effect of CYP450 inhibitors on miransertib exposure was performed using available data from the ARQ 092-101 clinical study. A subset of 32 participants with normal CYP2D6 expression who received doses of miransertib ranging from 10 mg qd to 270 mg qd-qow were evaluated. The majority of these participants (28/32) were taking one or more known CYP450 inhibitors (2D6, 3A4, 2C19, 2C9) concurrently with miransertib. The average AUC0-24 divided by dose for participants taking CYP inhibitors (17/32 2D6, 21/32 3A4, 13/32 2C19, and 12/32 2C9) was within 30% of the AUC0-24 of all participants regardless of inhibitor combination, with the lowest average AUC0-24 observed in participants taking no known inhibitors (4/32). Moreover, AEs known to be associated with miransertib such as hyperglycemia and rash were not observed more frequently in any subgroup. However, this analysis was conducted on a limited sample of participants, and to date, no formal DDI studies have been performed for miransertib.

Therefore, the following strong CYP inhibitors, inducers, and substrates are not permitted during the study:

- Strong CYP2D6 inhibitors and inducers
- Strong CYP3A4 inhibitors and inducers
- Strong CYP2C9 inhibitors and inducers
- Strong CYP2C19 substrates and inducers
- Grapefruit juice

See Appendix 3 for details.

# 6.8.4 Potential of Drug-Drug Interaction When Miransertib and Warfarin Are Coadministered

Warfarin is the standard treatment for participants at risk for developing DVT or PE. To date, no formal clinical studies have been conducted to assess the potential for DDI of miransertib with warfarin. Hence, the following assessment is based on in vitro CYP450 studies with miransertib, clinical experience of miransertib (monotherapy) in Phase 1 oncology studies, and literature data available for warfarin.

Miransertib is metabolized by CYP2D6, CYP2C9, and CYP3A4. Additionally, miransertib has been shown to inhibit CYP2C19, CYP2C9, and CYP2D6 with IC50 values of 4.0, 3.0,

and  $10.2~\mu\text{M}$ , respectively. Warfarin is also metabolized by CYP2C9, CYP3A4, and CYP1A2.

Because both agents are metabolized by CYP2C9 and CYP3A4, and miransertib is a moderate to strong inhibitor of CYP2C9, the continued use of warfarin for participants taking miransertib is not recommended. Also, sensitive substrates for CYP2C19 should be avoided or used with caution. See Appendix 3 for details.

For participants who show a clinical need for an antithrombolic agent, there are alternative therapies that do not have a high DDI risk based on CYP metabolism. Possible options include thrombin inhibitors such as argatroban that is minimally involved in CYP3A4/5 metabolism (in vitro) or dabigatran (not metabolized by any CYP450 enzymes). Dabigatran is a P-glycoprotein 1 (P-gp) substrate/inhibitor (Appendix 4); it should be noted that while miransertib is not a P-gp substrate, it has not been tested in P-gp inhibition studies.

#### 6.9 Potential Risks

Based on data from oncology and nononcology clinical studies, participants should be monitored for signs and symptoms of hyperglycemia, skin toxicities (rash maculopapular, rash, pruritus, dermatitis, etc.), stomatitis/mucosal inflammation, transaminase (ALT and AST) elevation, and diarrhea. These potential risks are generally consistent with the PI3K/AKT/mTOR pathway inhibitor class. The current safety information for miransertib can be found in the IB.

Also, based on nonclinical data it has been suggested that miransertib may cause a phototoxic reaction in some participants exposed to the drug and sunlight. The amount of miransertib that may be required to cause such reaction is unknown. All participants should be instructed to avoid exposure to sunlight, to use sunscreen to protect exposed areas of the body (eg, forehead, nose, lips, and hands), and to report symptoms that may be associated with phototoxic reaction (eg, redness, pruritus, swelling, blister formation).

There can be other drug-related risks factors that have not yet been reported.

### 7 SAFETY ASSESSMENTS

Adverse events will be assessed throughout study and categorized by the current version of CTCAE. Participants will be evaluated according to the Schedule of Events in Table 3 and Table 4. If clinically indicated, unscheduled laboratory tests and any clinical assessments or evaluations may be performed per the discretion of the investigator.

#### 7.1 Definitions

## 7.1.1 Adverse Event

AE means any untoward medical occurrence associated with the use of a drug in humans, whether considered drug related. An AE can therefore be any unfavorable and unintended sign (including an abnormal laboratory finding, for example), symptom, or disease temporally associated with the use of a medicinal product and does not imply any judgment about causality.

#### 7.1.2 Adverse Reaction

An adverse reaction is defined as any event for which there is a reasonable possibility that the drug caused the event.

## 7.1.3 Suspect Adverse Reaction

A suspected adverse reaction is defined as any AE for which there is a reasonable possibility that the drug caused the AE. Reasonable possibility means that there is evidence to suggest a causal relationship between the drug and the AE. Suspected adverse reaction implies a lesser degree of certainty about causality than adverse reaction, which means any AE caused by a drug.

## 7.1.4 Unexpected

An AE or SAR is considered "unexpected" if it is not listed in the IB or is not listed at the specificity or severity that has been observed. "Unexpected" also refers to AEs or SARs that are mentioned in the IB as occurring with a class of drugs or as anticipated from the pharmacological properties of the drug but are not specifically mentioned as occurring with the particular drug under investigation.

## 7.1.5 Serious

An AE or SAR is considered "serious" (an SAE) if, in the view of either the investigator or Sponsor, it results in any of the following outcomes: death, a life-threatening AE, in-patient hospitalization or prolongation of existing hospitalization, a persistent or significant incapacity or substantial disruption of the ability to conduct normal life functions, or a congenital anomaly/birth defect. Important medical events that may not result in death, be life-threatening, or require hospitalization may be considered serious when, based on appropriate medical judgment, they may jeopardize the participant and may require medical or surgical intervention to prevent one of the outcomes listed. An AE or SAR is considered "life-threatening" if, in the view of either the investigator or Sponsor, its occurrence places the participant at immediate risk of death.

## 7.1.6 Suspected Unexpected Serious Adverse Reaction (SUSAR)

All AEs that are determined by the investigator or by the Sponsor as having a reasonable suspected causal relationship (possibly, probably, or definitely related) to a study medication including placebo and that are both unexpected and serious are considered to be SUSAR and are subject to expedited regulatory reporting.

## 7.1.7 Hospitalization

Hospitalization is defined as a hospital admission that lasts more than 24 hours.

## 7.1.8 Study Medication-related Adverse Event or Serious Adverse Event

Study medication-related AE or SAE is defined as an AE or SAE that is related to the treatment with miransertib. A related AE or SAE is any AE or SAE considered related, probably related, or possibly related to miransertib.

## 7.1.9 Further Adverse Event and Serious Adverse Event Defining

Wherever possible, a specific disease or syndrome rather than individual associated signs and symptoms should be identified. However, if an observed or reported sign or symptom is not considered a component of a specific disease or syndrome by the investigator, it should be recorded as a separate AE.

Laboratory data are to be collected as stipulated in this protocol. Clinical syndromes associated with laboratory abnormalities are to be recorded as appropriate (eg, diabetes mellitus instead of hyperglycemia).

Scheduled hospitalizations or elective surgical procedures will not be considered as AEs or SAEs. Prolongation of a scheduled hospitalization can be considered an SAE.

Complications associated with scheduled procedures are considered AEs or SAEs.

Treatment-emergent AEs, including SAEs are events with the onset or the worsening of the severity that occurred at or any time after administration of the first dose and through 90 days after the administration of the last dose of the study medication.

Any AEs, including SAEs which are observed before administration of the study medication should be reported as medical history.

## 7.2 Responsibilities and Procedures

The responsibility for the safety of an individual participant lies in all cases with the investigator. This includes the timely review of all safety data obtained during the course of the study.

An investigator must instruct his/her participants to report any AE and SAEs they experience. Investigators must capture, evaluate, and document all AEs and SAEs occurring during a

participant's participation in the study, commencing with the first day of treatment and including the protocol-defined 30-day post-treatment follow-up period as source documents and on designated eCRF pages. These AEs/SAEs must be recorded in the EDC system of this study.

Investigators should assess AEs at each scheduled and nonscheduled visit, by the use of open-ended questioning, physical examination, and review of laboratory results. It is important to record all AEs and SAEs that result in temporary and permanent discontinuation of study medication, regardless of severity.

Investigators must report all SAEs, whether they are considered study medication related, to the Sponsor or designee within 24 hours from knowledge of the event (see Section 8.4).

In cases of SUSARs, Investigators are responsible for reporting to their local IRB/IEC as required by regulation; and the Sponsor or designee is responsible for notifying regulatory authorities and all relevant Investigators of SUSARs.

#### 7.3 Adverse Event and Serious Adverse Event Criteria

AEs and SAEs are evaluated and graded using current NCI CTCAE guidelines.

## 7.4 Serious Adverse Event Reporting

In the event of any new SAE occurring during the study, the investigator must notify the Sponsor or designee within 24 hours of becoming aware of the event by telephone, or by email. When an event is reported by telephone, a written report must be sent immediately thereafter by email. For names, addresses, telephone numbers for SAE reporting, see information included on the SAE Report Form. All written reports should be transmitted using the SAE Report Form, which must be completed by the investigator after specific completion instructions. The AE section of the eCRF must be completed. Relevant pages from the eCRF may be provided in parallel. Additional documents may be provided by the investigator, if available (for ex; laboratory results, hospital report, autopsy report). In all cases, the information provided on the SAE Report Form must be consistent with the data on the event that is recorded in the corresponding sections of the eCRF. The investigator must respond to any request for follow-up information or to any question the Sponsor or designee may have on the AE within the same timelines as described for initial reports.

The information provided on the SAE Report Form should be as complete as possible but contain a minimum of:

- A short description of the AE (diagnosis) and the reason why the AE was categorized as serious
- Participant identification and treatment (if applicable)
- Investigator's name and phone number (if applicable)
- Name of the suspect medicinal product and dates of administration

Assessment of causality

If all information about the SAE is not yet known, the investigator will be required to report any additional information within 24 hours as it becomes available.

All SAEs will be evaluated by the Sponsor's Medical Monitor or designee. The Sponsor will make an assessment of the expectedness of an SAE based on the criteria outlined in Section 8.1.4. In the case of a SUSAR, once all of the relevant information is compiled on the event, the Sponsor or designee will report the event to all pertinent regulatory authorities having jurisdiction over ongoing miransertib studies in an expedited manner (within 7 days or 15 days of knowledge) and to all Investigators involved in miransertib clinical studies.

The Investigators must in turn notify their governing IRB/IEC as required by regulation.

## 7.5 Posttreatment Safety Follow-up

In this study, the posttreatment safety follow-up period is defined as 30 days after the last dose of miransertib. All AEs occurring during the study period from the time of the first dose to the last day of the 30-day posttreatment follow-up period will be captured.

All participants will be followed for a minimum of 30 days after discontinuation of miransertib. All participants should be instructed to report AEs or SAEs occurring during the 30-day posttreatment safety follow-up period.

Unresolved study medication-related (see Section 8.1.8 for definition) AEs and SAEs at the time of treatment discontinuation or new study medication-related AEs and SAEs that occur during the 30-day safety follow-up period will be followed until they have, in opinion of the Investigator, resolved to baseline, have stabilized, or are deemed to be irreversible.

## 7.6 Grading of Severity

Each AE or SAE will be graded for severity according to the current NCI CTCAE version. The criteria can be found at http://ctep.cancer.gov/reporting/ctc.html.

For AEs not listed in the NCI CTCAE, a similar grading system should be used as follows:

- Grade 1 Mild AE
- Grade 2 Moderate AE
- Grade 3 Severe AE
- Grade 4 Life-threatening or disabling AE
- Grade 5 Death related to AE

For AEs that can be described by the NCI CTCAE guidelines, the current NCI CTCAE version Grade 4 (life-threatening or disabling AE) is assessed based on unique clinical descriptions of severity for each AE and these criteria may be different from those used for

the assessment of AE seriousness. An AE assessed as Grade 4 based on the NCI CTCAE Grades may or may not be assessed as serious based on the seriousness criteria.

## 7.7 Assessment of Causality

The relationship between an AE and miransertib will be determined by the investigator by his/her clinical judgment and the following definitions:

#### 7.7.1 Related

- The AE follows a reasonable temporal sequence from study medication administration and cannot be reasonably explained by the participant's clinical state or other factors (eg, disease under study, concomitant diseases, concomitant medications).
- The AE follows a reasonable temporal sequence from study medication administration and is a known reaction to the drug under study or its chemical group or is predicted by known pharmacology as a known reaction to agent or chemical group or predicted by known pharmacology.
- A related AE is any AE considered related, probably related, or possibly related to miransertib.

#### 7.7.2 Not Related

• The AE does not follow a reasonable sequence from study product administration or can be reasonably explained by the participant's clinical state or other factors (eg, disease under study, concurrent diseases, and concomitant medications).

#### 8 ASSESSMENT OF RESPONSE

Efficacy assessments are no longer being conducted in this protocol with the adoption of Amendment 7. Analyses of previously collected responses may be performed by the Sponsor.

#### 8.1 Measurable Disease

No longer applicable with the adoption of Amendment 7.

## **8.2** Response Evaluation

No longer applicable with the adoption of Amendment 7.

#### 9 PLANNED STATISTICAL METHODS

#### 9.1 General Considerations

Details of the statistical analyses presented below will be provided in the study's SAP. The SAP will be finalized before database lock. Any changes to the methods described in the plan will be described and justified in the final clinical study report.

All data listings, summaries, figures and statistical analyses will be generated using SAS version 9.4 or higher. Summaries will be presented by Part (A/B), Cohort (and by dose within, Cohort for AEs), and overall. Continuous variables will be summarized by the number of nonmissing observations, mean, median, standard deviation, minimum and maximum. Categorical variables will be summarized by presenting the frequency and percent. Percentages will be based on the number of nonmissing observations or the participant population unless otherwise specified. For each variable, all categories will be shown. Zero frequencies (but not the percent) within a category will be presented.

## 9.2 Analysis Populations

**Safety Population**: all patients who have received a dose of study medication.

## 9.3 Study Endpoints

Under this amendment, the endpoints for Part A and Part B have been combined to assess the safety and tolerability of miransertib in participants with PROS and PS based on the frequency, duration, and severity of AEs from the first dose of the drug through 90 days after the last dose of the drug.

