For Part B Cohort 1, 2, and 3, safety (eg, physical examination, vital sign measurements, clinical laboratory tests, use of concomitant medications, and collection of AE information) assessments will be performed at baseline, twice during the first cycle, and at each study visit thereafter. All clinical assessments and laboratory tests will be performed per the Schedule of Events [Table 3]

For Cohort 4, safety (eg, physical examination, vital sign measurements, clinical laboratory tests, use of concomitant medications, and collection of AE information) assessments will be performed every 3 months (Table 4). If clinically indicated, unscheduled laboratory tests and any clinical assessments or evaluations may be performed per the discretion of the investigator.

A single blood sample will be collected for CYP2D6 genotyping. The final clinical safety follow-up will be performed 30 days after the last dose of miransertib.

Miransertib is supplied as 5- and 10-mg capsules and should be swallowed whole (1 hour before or 2 hours after a meal). When medically necessary, the capsules can be opened and

sprinkled onto a small amount of sweetened semiliquid food (eg, apple sauce, chocolate syrup, or ice cream).

The study data and endpoints were reviewed by the Sponsor in 2020. It was concluded that the current data from this study would not be sufficient to establish efficacy for either the PROS or PS patients. As a consequence, Amendment 7 was written to remove all efficacy assessments, including the volumetric MRIs for the PROS patients, the CCTN photography for the PS patients, as well as to remove the functional assessments, among others.

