4.16 Adverse Events

AEs will be assessed by the frequency, duration and severity from the first dose of miransertib through 90 days after the last dose of the drug. Severity of AEs will be assessed by the current version of Common Terminology Criteria for Adverse Events (CTCAE). A treatment emergent adverse event (TEAE) is defined as follows:

- Any AE that has an onset on or after the first dose of study drug and before last dose of study drug + 90 days.
- Any pre-existing AE that has worsened in severity on or after the first dose of study drug and before the last dose of study drug + 90 days.

A treatment-related AE (TRAE) is defined as an AE as being related to miransertib.

The following tables will be presented for AEs:

- Overall incidence and the number of TEAEs, ≥ grade 3 TEAEs, serious AEs (SAEs), TRAEs, serious TRAEs, TEAEs leading to early study withdrawal, and deaths (TEAEs leading to death and AEs leading to death).
- TEAEs by SOC and PT, incidence and number of events
- TRAEs by SOC and PT, incidence and number of events
- Serious TEAEs by SOC and PT, incidence and number of events
- Serious TRAEs by SOC and PT, incidence and number of events
- Serious TRAEs resulting in death by SOC and PT, incidence and number of events
- Serious non-TRAEs by SOC and PT, incidence and number of events
- Non-serious TEAEs by SOC and PT, incidence and number of events
- Non-serious TEAEs by SOC and PT, incidence >5% in one or more cohorts and number of events
- TEAEs by SOC, PT, and maximum toxicity, incidence
- TEAEs leading to early study withdrawal by SOC and PT, incidence
- TEAEs reported in ≥10% of participants by PT, sorted by decreasing incidence of PT

Template: WCT-TP-ST-005-005 Page 17 of 24 Effective Date: 15-Apr-2016 Confidential

- TRAEs reported in ≥10% of participants by PT, sorted by decreasing incidence of PT
- Serious TEAEs reported in ≥5% of participants by PT, sorted by decreasing incidence of PT
- All AEs resulting in death by PT, sorted by decreasing incidence of PT
- Listing of TEAEs
- Listing of SAEs
- Listing of TEAEs leading to early study withdrawal
- Listing of subjects with TEAEs resulting in treatment interruption
- Listing of subjects with TEAEs resulting in treatment discontinuation
- Listing of AEs leading to death

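### The only endpoint and both TEAE definitions run to 90 days after last dose, but planned AE capture stops at 30 days and Part B schedules no later visit

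*Protocol*

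**What the plan says.** **Ninety days.** The endpoint, in the same words in the protocol synopsis, protocol 2.3 and 9.3 and SAP 2.2.1, is the frequency, duration and "severity of AEs from the first dose of the drug through 90 days after the last dose of the drug". Protocol 7.1.9 defines treatment-emergent events as those that start or worsen from first dose "through 90 days after the administration of the last dose of the study medication". SAP 4.16 counts any event with "onset on or after the first dose of study drug and before last dose of study drug + 90 days", and applies the same limit to worsening of pre-existing events.

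**Thirty days.** Protocol 7.5 says that "the posttreatment safety follow-up period is defined as 30 days after the last dose of miransertib". It limits capture of AEs to the end of that period, and limits the instruction to participants to report AEs in the same way. Protocol 7.2 sets the investigator's recording duty as "commencing with the first day of treatment and including the protocol-defined 30-day post-treatment follow-up period". Protocol 2.2 states: "The final clinical safety follow-up will be performed 30 days after the last dose of miransertib".

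**Schedules.** For Part B, protocol section 4 and Tables 3 and 4 end at the 30-day safety visit, whose window is 30 days or more with no upper limit. For Part A, section 4 sends ongoing participants to Annex 1. The schedule there has a further follow-up column at 3 months (±14 days) with AEs marked. The Annex 1 end-of-treatment table has no such column, but its footnote refers to a follow-up at three cycles.

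**Reporting.** SAP 4.4 presents summaries by Part, by Cohort and overall.

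**The concern.** After Amendment 7 this is a safety-only study, so the TEAE tables are its result. A table built on the 90-day definition tells the reader that events were looked for over 90 days after last dose. In Part B the protocol plans to look for about a third of that time. Few events in the last 60 days could mean that few occurred or that nobody asked, and the reader could not tell which.

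There is a second, conditional issue. If Part A participants did attend a three-month visit, the same TEAE rule would be applied to about 30 days of planned post-treatment collection in Part B and about three months in Part A. The Overall column would then mix the two.

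**Working it through.** The plan gives no figure for this point, so there is none to reproduce. The check compares the stated windows and measures the gap in calendar time. It does not estimate events.

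**1. Is there any route to new onsets on days 31 to 90 in Part B?**
- Scheduled visits: none after the 30-day visit (section 4, Tables 3 and 4).
- Minimum follow-up (7.5): "All participants will be followed for a minimum of 30 days after discontinuation of miransertib". Together with the open-ended visit window, this permits later reports but does not require them.
- Following events to resolution (7.5): this covers drug-related events unresolved when treatment stops, and new ones that "occur during the 30-day safety follow-up period will be followed until they have, in opinion of the Investigator, resolved to baseline", or that stabilise or are judged irreversible. It tracks events that began by day 30. It does not seek later onsets.
- Serious events: 7.4 requires notification of any new SAE during the study and states no day limit there, whereas 7.2 ends the recording duty for AEs and SAEs at 30 days. The text is ambiguous.

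New non-serious onsets on days 31 to 90 are therefore not systematically sought. For serious onsets the documents can be read either way.

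**2. Post-dose coverage in Part B (planned minimum).**
- Defined window 90 days; planned capture 30 days.
- 30/90 = 33.3%, leaving 90 − 30 = 60 days.

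**3. The 60 days as a share of the whole endpoint window.** With T days of continuous treatment in 28-day cycles, the share is 60/(T + 90). The synopsis expects most participants to receive 3 to 48 cycles; 12 cycles is added as a midpoint for illustration.

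| Cycles | T (days) | 60/(T + 90) | Share |
|---|---|---|---|
| 3 | 84 | 60/174 | 34.5% |
| 12 | 336 | 60/426 | 14.1% |
| 48 | 1344 | 60/1434 | 4.2% |

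The documents give no distribution of treatment duration, so none of these rows can be called typical. The gap weighs most on participants who stop early.

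**4. Part A, only if the Annex 1 visit took place.** Two assumptions are needed: the visit is timed from last dose, and one visit recovers every onset back to day 30.
- Three months read as 90 days: 90 ± 14 gives days 76 to 104. Coverage is 76/90 = 84.4% up to 100%, a gap of 0 to 14 days.
- Three cycles: 84 ± 14 gives days 70 to 98. Coverage is 70/90 = 77.8% up to 100%, a gap of 0 to 20 days.

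**5. Drug still present after day 30?** Protocol 1.3.1.2 estimates a half-life of 40 to 60 hours and says that it could not be determined accurately. Thirty days is 720 hours: 720/60 = 12 and 720/40 = 18 half-lives.

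**6. Day-90 boundary.** Protocol 7.1.9 includes day 90, while SAP 4.16 stops before it. This is a one-day difference.

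**The case against.** **The effect may be negligible.** Thirty days is 12 to 18 estimated half-lives, the analysis is descriptive, and no test or decision threshold depends on it. This stands as a reason not to overstate the point. It does not remove it: TEAEs count all events whatever their cause, so drug clearance does not close the gap, and the documents give no off-drug event rate from which to show that the effect is small.

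**Part A and Part B definitely have unequal windows.** A reader might infer this from Annex 1, but the documents do not establish it. Protocol 2.2, 7.2 and 7.5 are not limited to Part B, and 7.5 speaks of all participants. Under those sections Part A capture also ends at 30 days. The three-month column conflicts with them and is missing from the end-of-treatment table. The inequality depends on whether the visit was carried out.

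**Nothing at all is collected in Part B after day 30.** This too goes further than the text. The open-ended visit window allows irregular later reports, and 7.4 may reach later SAEs.

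**The SAP changed nothing, so it had nothing to record.** This is fair. SAP 4.16 carries over the protocol's 90-day window, and the silence of SAP section 7 is not evidence of an error.

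**A 30-day table does not make the Parts comparable.** This is also true. Treatment length varies widely, and Cohort 4 enrols people already exposed to miransertib. The synopsis and protocol 2.1 also say that patients will move to new miransertib programs, so for some of them days 31 to 90 could be on-drug time elsewhere. The added tables correct the ascertainment window only.

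**Conclusion.** The contradiction is in the current text of both documents: a 90-day endpoint and TEAE definition against 30-day planned capture. In Part B the planned minimum covers 30 of 90 post-dose days. The remaining 60 days make up 34.5% of the endpoint window after 3 cycles and 4.2% after 48, assuming continuous treatment. These are shares of calendar time, not of expected events. Unequal windows between Part A and Part B are possible but conditional on the Annex 1 visit.

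The effect on TEAE incidence cannot be computed from the documents and may be small. A claim that incidence is materially understated would go beyond them. The point is worth correcting before the tables are produced, because tables labelled 90 days would misdescribe what was systematically ascertained. It does not invalidate the safety analysis.

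**What to change.** **Reconcile the passages.** The 90-day text is in the protocol synopsis, 2.3, 7.1.9 and 9.3 and in SAP 2.2.1 and 4.16. The 30-day text is in protocol 2.2, 7.2, 7.5, section 4 and Tables 3 and 4. The SAE wording in 7.4 should be settled against 7.2, and the three-month column in Annex 1 against its end-of-treatment table and the three-cycle footnote. Which follow-up rule should apply is for the sponsor to decide, not this review.

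**In SAP 4.16:**
1. Add TEAE tables by Part and Overall for onset or worsening from first dose through 30 days after last dose. This is the window with planned collection in both Parts.
2. Keep the 90-day tables as the stated endpoint, with a footnote that Part B had no scheduled AE collection after the 30-day visit.
3. Flag onsets on days 31 to 90, by Part, in the TEAE listing that is already planned.
4. Use the same rule for day 90 in both documents.

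Record the added tables in SAP section 7.

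**Cost.** SAP wording, one extra set of tables and a flag in an existing listing. The SAP change needs no new data, and no recorded event leaves the 90-day tables. The drawback is that two TEAE windows appear in the report, so each table title must state its window.
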